1. SYNOPSIS

Long Study Title	An Investigation into the Efficacy of Online Cognitive Behaviour Therapy for Insomnia (“Sleepio”) for Stroke Survivors	
Short Study Title (to be used on participant-facing documents, if applicable)	Improving sleep in rehabilitation after stroke (INSPIRES)	
Nature of Study Participants	Stroke survivors	
Intended number of participants	86	
Design	Randomised controlled	
Location	In the participant's home / online	
	Objectives	Outcome Measures
Primary	The primary objective of this study is to assess whether self-reported sleep quality in stroke survivors is improved following online Cognitive Behavioural Therapy for Insomnia (“Sleepio” programme).	The primary outcome measures for this study will be the change in Sleep Condition Indicator score following completion of the programme.
Secondary	
The secondary objectives are to assess changes in measures of sleep quality and self-reported measures of quality of life and anxiety following the intervention and at 8 week follow up.
 
To assess the cost-effectiveness of online CBT-I in stroke survivors when compared to a brochure of sleep hygiene information.
	
Changes in sleep fragmentation and wake after sleep onset, assessed with actigraphy, sleep onset latency assessed through the sleep diaries, anxiety and depression using the PHQ9 and GAD7, quality of life using the Stroke impact scale-8 and Euroqol-5 Dimensions- 5 Levels (EQ-5D-5L)
 
Changes in healthcare costs during the 8-week follow up.

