3. STUDY DESIGN

The study will be a single-blinded randomised controlled trial involving the completion of a six-week digital CBT-I programme. Following written informed consent, participants will be posted baseline questionnaires to complete and an actigraphy monitor to record objective sleep measures for one week. After this, participants will be randomised to CBT-I or control using an online randomisation software (rando.la) with minimisation of between group differences based on age and baseline self-reported sleep quality (Sleep Condition Indicator (SCI) score). The control group will be given access to an online sleep diary to complete daily for one week. They will also be given a brochure containing sleep hygiene information. 8 weeks later they will be asked to complete the online sleep diary again for one week.

Participants allocated to Sleepio will complete daily online sleep diaries for the duration of the study and will receive weekly online CBT-I sessions as part of the programme. Both groups will complete their programmes at home.

Participants will be sent the questionnaires and actigraphy monitor again to be worn for another week immediately following completion of the programme (Sleepio) or following the 6-week sleep diary (control) and at 8 weeks follow up. At 8 weeks follow up, participants in the intervention group will also be sent a debriefing questionnaire to get feedback on the programme and the research study.

Participants allocated to the control group will be sent a web link and activation code for the Sleepio programme following completion of the 8 week follow up.

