5.4. Randomisation

Participants will be randomised into the CBT-I or control group based using an online randomisation software (rando.la) with minimisation of between group differences based on baseline SCI score and age.

All participants randomised to the control group will be offered the opportunity to undergo the Sleepio programme after completion of the 8-week follow up.

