8. STATISTICS AND ANALYSIS

8.1. Description of Statistical Methods

The efficacy of Sleepio will be assessed by comparing the SCI scores of the intervention and control groups from baseline to immediately post-intervention, following an intention to treat analysis approach. Changes in the primary outcome measure from baseline to post-intervention will be assessed with analysis of variance (ANOVA) (or linear mixed model or non-parametric equivalents if necessary) with inclusion of baseline score as a covariate.

Secondary outcomes will be assessed with ANOVA (or linear mixed model or non-parametric equivalents if necessary). EQ-5D-5L responses will be converted into utility values using population preferences (van Hout et al., 2012) and combined with survival information to calculate Quality Adjusted Life-Years (QALYs). All resource use will be valued using 2018/19 unit costs obtained from healthcare compendiums, (Curtis and Burns 2018) NHS reference costs, (<https://improvement.nhs.uk/resources/reference-costs/>) and British National Formulary (<https://www.bnf.org/>). Costs of CBT-I will be obtained from the trial.

An incremental analysis will be performed, assessing the differences in costs between the two interventions and dividing by the difference in QALYs gained in order to generate an incremental cost-effectiveness ratio (ICER). ICERs will be estimated using an NHS perspective. The 10 000 bootstrapped pairs of incremental costs and incremental QALYs will be plotted on cost-effectiveness planes to display the uncertainty in the estimated ICER. Cost-effectiveness acceptability curves (CEACs) will be derived to display the probability of the CBT treatment being cost-effective, as the ceiling ratio for the maximum acceptable cost-effectiveness ratio varies from £0 to £85 000 per QALY gained.

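### Section 8.1 names a baseline covariate for the primary outcome only; stating none for secondary outcomes and incremental QALYs gives up precision, without biasing the estimates

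*Combined protocol and SAP*

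**What the plan says.** All references are to the combined protocol and SAP.

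- **Primary outcome (Section 8.1).** Change in SCI is analysed by ANOVA, with a mixed model or non-parametric method in reserve, "with inclusion of baseline score as a covariate".
- **Secondary outcomes (Section 8.1).** The next sentence repeats the list of methods without that clause: "Secondary outcomes will be assessed with ANOVA (or linear mixed model or non-parametric equivalents if necessary" (the bracket and the sentence end there).
- **Economic analysis (Section 8.1).** The ICER is formed by "assessing the differences in costs between the two interventions and dividing by the difference in QALYs gained". Uncertainty is shown by resampling: "The 10 000 bootstrapped pairs of incremental costs and incremental QALYs will be plotted on cost-effectiveness planes". No adjustment for baseline utility or baseline cost is mentioned, and the section does not say whether QALYs are raw area under the curve or net of baseline.
- **Form of the secondary outcomes (Section 1).** They are worded as changes, for example "Changes in sleep fragmentation and wake after sleep onset, assessed with actigraphy" and "Changes in healthcare costs during the 8-week follow up".
- **Baseline data (Sections 3, 5.5 and 5.6).** GAD-7, PHQ-9, SIS-8, EQ-5D-5L, an 8-week recall of healthcare contacts (modified CSRI), actigraphy and a sleep diary are collected first. Then: "After this, participants will be randomised to CBT-I or control using an online randomisation software (rando.la" (bracket closed there). The baseline assessments are repeated at the 8-week follow-up.
- **Balance (Section 5.4).** Allocation is made "with minimisation of between group differences based on baseline SCI score and age". Baseline utility, cost and the other secondary measures are not minimisation factors.

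**The concern.** Two adjacent sentences in Section 8.1 give the same methods, and only the first includes the baseline covariate. An analyst who follows the text would leave the baseline out for every secondary outcome and for incremental QALYs, although the values are already in hand.

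With about 34 completers per arm, secondary effects and incremental QALYs would then be estimated less precisely than the collected data allow. Cost-effectiveness is a named secondary objective, and acceptability curves are planned up to £85 000 per QALY, so the precision of the QALY difference matters. The silence also leaves the choice between adjusted and unadjusted analyses open until the data have been seen.

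**Working it through.** **Plan's own figure.** Section 8.2 gives d = 0.7, alpha 0.05, power 80%, 1:1. A two-sided two-sample t-test needs 33.02 per arm, rounded up to 34, so 68 in total, as stated. The power at 34 per arm is 81.2%. This figure is not in question; 34 per arm is used below.

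**Assumptions.** The documents give no correlations or SDs. Let r be the baseline-outcome correlation, with equal SDs at each time.

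**1. Secondary outcomes.** Relative variances of the arm difference are 1 (post-score ANOVA), 2(1 − r) (change-score ANOVA) and 1 − r² (ANCOVA). Hence ANCOVA/change = (1 + r)/2 and ANCOVA/post = 1 − r².

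| r | ANCOVA/change | cut | ANCOVA/post | cut |
|---|---|---|---|---|
| 0.3 | 0.65 | 35% | 0.91 | 9% |
| 0.5 | 0.75 | 25% | 0.75 | 25% |
| 0.7 | 0.85 | 15% | 0.51 | 49% |

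On the change-score reading, 68 participants are worth 68(1 + r)/2 = 44, 51 and 58 analysed by ANCOVA.

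**2. Cost of estimating the slope.** With 68 participants and a normal covariate, the ANCOVA variance rises by about 1/64 = 1.6%. At r = 0.3 against post-score ANOVA the cut becomes 1 − 0.91 × 65/64 = 7.6%. At r = 0.7 against change-score ANOVA it becomes 1 − 0.85 × 65/64 = 13.7%. The conclusion does not change.

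**3. QALYs.** Assume utilities measured at weeks 0, 6 and 14 (a six-week programme, then 8 weeks), equally correlated at r. The trapezium weights, in units of 1/52, are 3, 7, 4. Subtracting baseline utility over all 14 weeks gives −11, 7, 4. The variances, up to a common factor, are:

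- raw: 9 + 49 + 16 + 2r(21 + 12 + 28) = 74 + 122r
- net: 121 + 49 + 16 + 2r(−77 − 44 + 28) = 186(1 − r)
- adjusted for baseline utility: 65(1 − r²) + 56r(1 − r) = (1 − r)(65 + 121r)

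| r | raw | net | adjusted | cut against net | cut against raw |
|---|---|---|---|---|---|
| 0.5 | 135.0 | 93.0 | 62.75 | 33% | 54% |
| 0.6 | 147.2 | 74.4 | 55.04 | 26% | 63% |
| 0.7 | 159.4 | 55.8 | 44.91 | 20% | 72% |
| 0.8 | 171.6 | 37.2 | 32.36 | 13% | 81% |

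A simulation at 34 per arm with an assumed utility SD of 0.25 agrees. At weeks 0, 6 and 14 the SE of the raw difference falls from 0.0136 to 0.0093 (r = 0.5) and from 0.0153 to 0.0067 (r = 0.8). The mean error over repeated randomisations was at most about 0.0002 QALY, adjusted or not. If follow-up instead ends at week 8 (assessments at weeks 0, 6 and 8), the cuts are 30 to 12% against net and 67 to 87% against raw.

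**4. Costs.** Against a plain cost difference the cut is 1 − (1 − r²) × 65/64: −1.6% at r = 0 (slightly worse), 2.5% at r = 0.2, 15% at r = 0.4 and 35% at r = 0.6. If change in cost is analysed with equal SDs, the cuts at r = 0/0.2/0.4/0.6 are 50/40/30/20%, before the slope cost. Equal SDs are doubtful: the baseline is a recall questionnaire and in-trial contacts come from a log book. If the follow-up SD is 1.5 times the baseline SD, the ratio is 2.25(1 − r²)/(3.25 − 3r) and the cuts fall to 31/18/8/1%.

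**The case against.** **Silence is not exclusion.** Section 1 words the primary outcome as a change too, and Section 8.1 calls its baseline-adjusted analysis an ANOVA. The same word for secondary outcomes could therefore carry the same covariate. This stands: a reader might infer that the plan rules out adjustment, and the text does not say that. But it does not provide for it either, and the loss arises under both the change-score and the post-score reading.

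**A mixed model may carry the baseline.** It could recover some or all of the loss. Section 8.1 keeps it in reserve and does not say how the baseline would enter.

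**The size is not known.** This also stands. At the plan's own d = 0.7 (set for SCI, and no power is claimed for secondary outcomes), change-score against ANCOVA power with 34 per arm is 67 against 85% at r = 0.3, 81 against 91% at r = 0.5, and 96 against 98% at r = 0.7. The loss can be material or slight.

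**Tempting stronger readings.** A reader might infer that the unadjusted ICER is biased because utility and cost are not minimised. With complete data, randomisation makes the differences unbiased over repeated trials, and the bootstrap carries the extra variance. A chance baseline imbalance that moves the single realised ICER is that same variance seen conditionally, not a second harm. A reader might also extend the loss to costs; the documents give no correlation to support that.

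**Conclusion.** The point holds for secondary outcomes and incremental QALYs as a loss of precision that can be avoided at almost no cost. The direction is the same at every assumed correlation (0.3 to 0.7 for secondary outcomes, 0.5 to 0.8 for QALYs), on either reading of the outcome and with follow-up ending at week 14 or week 8. The size rests on assumed correlations and equal SDs: variance cuts of 15 to 35% against change scores, 9 to 49% against post scores, 13 to 33% against net QALYs and 54 to 81% against raw QALYs. For costs no loss is established. The primary analysis and the sample size are unaffected. This should be changed, but it does not threaten the validity of the trial.

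**What to change.** State in Section 8.1:

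1. Each continuous secondary outcome is analysed by ANCOVA or a linear mixed model with its own baseline value as a covariate, as for the primary outcome. If a non-parametric method is needed, a rank-based ANCOVA using the baseline is used.
2. How QALYs are calculated: assessment times, and raw area under the curve or net of baseline.
3. Incremental QALYs are estimated by regression on arm and baseline EQ-5D-5L utility, refitted within each of the 10 000 bootstrap samples.
4. Optionally, incremental costs are adjusted for baseline CSRI cost in the same way. This costs about 1 to 2% of precision if the correlation is near zero, so the choice should be made in advance.

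The cost is a few sentences and one model term per outcome. No new data, visits or participants are needed.

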5.5. Baseline Assessments

After the signed consent form has been received by the researchers, the participant will be sent the GAD-7, PHQ-9, SCI, Stroke Impact Scale-8, Stroke Efficacy questionnaire and EQ-5D-5L to complete. Participants will also receive a questionnaire asking them to recall over the last 8 weeks all the contacts they have had with the healthcare service. This will be a modified version of the Client Service Receipt Inventory (CSRI).

We will also ask them to wear an actigraphy monitor on their wrist for one week and to complete a sleep diary at the same time. We will provide them with a prepaid envelope to send the materials back.

We will also record demographic variables including; age, sex, partner status, whether they share a bed, medications, employment status and date of stroke.

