5.6. Subsequent Assessments

Participants randomised to the intervention group will receive access, via web link and activation code to the digital CBT-I programme “Sleepio”. This programme will require the participant to keep a daily sleep diary and engage in weekly sessions comprising weekly CBT-I content. Participants randomised to the control group will be given access to an online sleep diary to complete for one week. They will also receive a brochure with sleep hygiene information and then will be asked to complete the online sleep diary again 8 weeks later.

During the trial, participants will be asked to keep a record, in a specially designed log book, of their contacts with the healthcare service.

Upon completion of the programme, participants will once again be sent questionnaires to complete (PHQ-9, GAD-7, SIS-8, Stroke Efficacy questionnaire and EQ-5D-5L), in addition to the wrist worn actigraphy monitor and the sleep diary to use for one week.

At 8 weeks follow up, all assessments conducted as baseline will be repeated and the intervention group will complete a debriefing feedback questionnaire.

6. Feasibility and Adverse events

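### Section 8.1 names no adjustment of incremental QALYs for baseline EQ-5D-5L utility, although that utility is collected and adjustment would make the secondary economic analysis more precise

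*Combined protocol and SAP*

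**What the plan says.** Section 8.1 analyses the primary outcome "with inclusion of baseline score as a covariate". The next sentence names no covariate: "Secondary outcomes will be assessed with ANOVA (or linear mixed model or non-parametric equivalents if necessary". For the economic analysis, EQ-5D-5L utilities are "combined with survival information to calculate Quality Adjusted Life-Years (QALYs", and the ICER comes from "assessing the differences in costs between the two interventions and dividing by the difference in QALYs gained". Uncertainty is shown by resampling: "The 10 000 bootstrapped pairs of incremental costs and incremental QALYs will be plotted on cost-effectiveness planes". The acceptability curve then runs over ceilings from £0 to £85,000 per QALY. No section names a baseline-utility term for QALYs.

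The covariate is available. At baseline (Section 5.5), "the participant will be sent the GAD-7, PHQ-9, SCI, Stroke Impact Scale-8, Stroke Efficacy questionnaire and EQ-5D-5L to complete". EQ-5D-5L is asked again after the programme (Section 5.6: "questionnaires to complete (PHQ-9, GAD-7, SIS-8, Stroke Efficacy questionnaire and EQ-5D-5L") and at the 8-week follow-up, when the baseline assessments are repeated. It does not enter the allocation, which uses "minimisation of between group differences based on baseline SCI score and age" (Section 5.4; Section 3 gives the same two factors).

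**The concern.** A participant's baseline utility is part of the area under their utility curve and also predicts their later utilities. With about 34 participants per arm, a chance difference between arms at baseline passes into an unadjusted QALY difference. The variance that baseline utility could explain stays in the estimate. The cloud of bootstrapped pairs is then wider along the QALY axis than the collected data require. The plan already adjusts the SCI for its baseline value, and the same step for QALYs needs no new data. At stake is the precision of one secondary objective, cost-effectiveness. The primary analysis and the sample size are untouched.

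**Working it through.** **1. The plan's own figure.** Section 8.2 asks for 68 full datasets at d = 0.7, alpha 0.05 and 80% power. A two-sided two-sample t-test (sidedness is not stated) needs 33.02 per arm, rounded up to 34, so 68 in total. This agrees, and n = 34 per arm is used below.

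**2. Assumptions not in the documents.** Utility has the same SD at each visit (0.20 where an absolute size is needed) and the same correlation ρ between any two visits, 0.5 to 0.8. All participants survive. Assessments fall at weeks 0 and 6 and at a final visit. The text can be read as placing that visit 8 weeks after the programme (week 14) or at week 8, so both are shown.

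**3. Weights (trapezoid rule, in weeks; divide by 52 for years).** Week 14: 3, 7, 4. Week 8: 3, 4, 1. For change from baseline, subtract the horizon from the first weight: −11, 7, 4 and −5, 4, 1.

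**4. Variance.** In units of SD²/52²:
- V = w0² + w1² + w2² + 2ρ(w0w1 + w0w2 + w1w2)
- slope on baseline utility: b = w0 + ρ(w1 + w2)
- adjusted variance = V − b², so the share removed is b²/V

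| Final visit | ρ | Raw V | Raw b | Change V | Change b | Adjusted V | Removed from raw | Removed from change |
|---|---|---|---|---|---|---|---|---|
| Week 14 | 0.5 | 135 | 8.5 | 93 | −5.5 | 62.75 | 54% | 33% |
| Week 14 | 0.8 | 171.6 | 11.8 | 37.2 | −2.2 | 32.36 | 81% | 13% |
| Week 8 | 0.5 | 45 | 5.5 | 21 | −2.5 | 14.75 | 67% | 30% |
| Week 8 | 0.8 | 56.4 | 7 | 8.4 | −1 | 7.4 | 87% | 12% |

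The adjusted variance is the same from either starting point, because the two QALY versions differ only by a multiple of the covariate. The percentages do not depend on the SD. At ρ = 0.3 (week 14) adjustment still removes 36% from raw and 46% from change.

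**5. Absolute size.** With SD 0.20, the SE of the baseline difference is 0.20 × √(2/34) = 0.0485, and the SE of the incremental QALY is 0.0485 × √V / 52. Raw / change / adjusted:
- Week 14: 0.0108 / 0.0090 / 0.0074 (ρ 0.5); 0.0122 / 0.0057 / 0.0053 (ρ 0.8).
- Week 8: 0.0063 / 0.0043 / 0.0036 (ρ 0.5); 0.0070 / 0.0027 / 0.0025 (ρ 0.8).

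**6. One-SE baseline imbalance.** The raw QALY difference moves by 0.0485 × b / 52: 0.0079 to 0.0110 (week 14) or 0.0051 to 0.0065 (week 8). The raw and change versions move apart by imbalance × horizon, whatever ρ is: 0.0485 × 14/52 = 0.0131, or 0.0485 × 8/52 = 0.0075 QALY. At £85,000 per QALY, before rounding, that is £1,110 or £634.

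**7. Allowance for minimisation (week 14).** Suppose SCI and age explain 30% of utility variance at each visit and are perfectly balanced. Between-arm differences then have variance 0.7 and covariance ρ − 0.3 in place of 1 and ρ. Adjusting for baseline utility alone removes 30% to 73% (raw) or 42% to 17% (change) for ρ 0.5 to 0.8. With SCI and age also in the model:
- ρ 0.5: 76.2 (raw) and 93 (change) both fall to 76.2 − 4.3²/0.7 = 49.8, so 35% and 46% are removed.
- ρ 0.8: 112.8 and 37.2 both fall to 112.8 − 7.6²/0.7 = 30.3, so 73% and 19% are removed.

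In this scenario the utility-only slope (8.5 at ρ 0.5) over-corrects relative to the slope given the factors (4.3/0.7 = 6.1). That is why SCI and age belong in the model.

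**The case against.** The best reply is that nothing in Section 8.1 is wrong. Randomisation protects the QALY difference from systematic bias, a participant-level bootstrap would display the extra variance honestly, and minimising on SCI and age may indirectly limit utility imbalance. All of that stands, and it confines the point to precision and chance imbalance in one secondary analysis. It does not remove the point: the bootstrap shows the wider cloud without narrowing it, and the gain survives a generous allowance for minimisation.

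A reader might infer more in three ways that the documents do not support.
- **Two rival QALY definitions.** The synopsis speaks of changes in EQ-5D-5L, but as a quality-of-life outcome. The phrase about QALYs gained in 8.1 describes the ICER denominator. No section clearly defines a change-from-baseline QALY, and combining utilities with survival fits a raw area under the curve. The gap between the versions matters only if the analyst were to use the change version.
- **A loss of £1,110.** That figure takes the longer horizon, an assumed SD of 0.20, a one-SE imbalance and the top of the ceiling range. It falls to £634 with a week-8 visit and shrinks in proportion at lower ceilings.
- **A distorted acceptability curve.** The curve depends on costs and QALYs jointly. The documents give no incremental cost or cost variance, so no effect on it can be shown.

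**Conclusion.** The point holds as a worthwhile improvement to the secondary economic analysis. It is not an error and not a source of bias. With equal correlation of 0.5 to 0.8, adjusting for baseline utility cuts the variance of the incremental QALY by 54% to 81% (week 14) or 67% to 87% (week 8) against the raw area under the curve, which is the more natural reading of 8.1. Against a change-from-baseline QALY the gain is smaller: 33% to 13% or 30% to 12%. The direction is the same in every scenario examined. The absolute figures are less secure because they scale with the assumed SD: the gap between versions after a one-SE imbalance is 0.0098 to 0.0196 QALY at week 14 for SD 0.15 to 0.30. The sample size of 68 and the primary analysis do not change.

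**What to change.** Add to Section 8.1 that incremental QALYs will be estimated by regression on arm, baseline EQ-5D-5L utility and the minimisation factors (baseline SCI and age). The regression is refitted in each of the 10,000 bootstrap replicates, with participants resampled within arm and each participant's costs and QALYs kept paired. State a simple rule for missing baseline utility, set without regard to allocation. Because the adjusted estimate is the same for a raw or a change-from-baseline QALY, this sentence also settles any doubt about which is meant.

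The cost is a sentence or two of text and a few lines of code, with no new data, visits or participants. The downside is that the adjusted ICER may turn out less favourable than the unadjusted one, which is a reason to fix the choice before the data are seen.
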